5. STUDY DESIGN

5.1 Justification of Study Design

The TENEO 317 Model 2 excimer laser workstation received CE Mark status in Europe in 2017 and is currently running version 1.28 software (SW). The difference between the EU version 1.28 and the version 1.28 US SW is that the version 1.28 US SW will have software treatment capabilities other than myopic LASIK with or without astigmatism that will be disabled on all Technolas TENEO 317 Model 2 systems to be used in this myopia/myopic astigmatism study.

A retrospective post-CE Mark chart review provides evidence of the safety and effective performance of the TENEO 317 Model 2 excimer laser running PROSCAN ver. 1.27.2 SW for completing LASIK surgeries on myopic eyes with or without astigmatism through 1 month of follow-up with 518 eyes treated at 10 sites in Europe, Middle East and Africa.³³ Of the 518 eyes enrolled in the chart review, 72 eyes had spherical myopia and 446 eyes had myopic astigmatism.

In the chart review report, 93% of subject eyes were 20/20 or better at ≥ 1 mo, and 99% were 20/32 or better at ≥ 1 mo. Further, 100% of subject eyes had uncorrected distance visual acuity of 20/40 or better post-surgery.

The Technolas TENEO 317 Model 2 aspheric ablation PROSCAN version 1.27.2 software was the subject of a post-market study that demonstrated excellent results for spherical correction and showed a slight under-correction for cylinder. As a result, the laser's internal cylinder conversion factor for the PROSCAN version 1.27.2 software was increased to compensate for cylindrical under-correction, while the spherical correction component remained unchanged. The resulting revised aspheric ablation PROSCAN version 1.28 US software is the subject of this study.

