5.3 Selection of Study Population

- 5.3.1 Eligibility^{40, 41}
- 5.3.1.1 Inclusion Criteria:
- 1. Are 22 years of age or older.
- 2. Have read, understood, and signed an informed consent form (ICF).
- 3. Have demonstrated stable refraction (i.e., a change of ≤ 0.5 D in sphere and cylinder) for a minimum of 12 months prior to surgery, verified by consecutive refractions and/or medical records or prescription history.
- 4. Have myopic refractive error with or without astigmatism; sphere between -1.0 D and -10.00 D, cylinder between 0.0 D and -3.0 D; with a manifest refraction spherical equivalent (MRSE) between -1.0 D and -11.50 D.
- 5. Have uncorrected distance visual acuity (UDVA) of 20/40 or worse.
- 6. Have manifest best spectacle corrected distance visual acuity (BSCVA) of 20/25 (logMAR 0.1) or better in an operative eye.
- 7. Have less than or equal to 0.50 D spherical equivalent (SE) difference between cycloplegic and manifest refractions at Visit 1 (Pre-operative).
- 8. Have normal corneal topography as determined by the Investigator.
- 9. Have discontinued use of contact lenses for at least 2 weeks (for hard or toric lenses) or 3 days (for soft contact lenses) prior to the pre-operative examination, and through the day of surgery.
- 10. All contact lens wearers must demonstrate a stable refraction (within \pm 0.5 D), as determined by MRSE, on two consecutive examinations at least 1 week apart, in an eye to be treated and the axis of cylinder should not differ by more than 15 degrees.
- 11. Have the ability to lie flat without difficulty.
- 12. Are willing and able to comply with the schedule for all post-surgery follow-up visits.

5.3.1.2 Exclusion Criteria:

- 1. Subjects for whom the combination of their baseline corneal thickness and the planned operative parameters for the LASIK procedure would result in treatment depth less than 250 microns from corneal endothelium.
- 2. Eyes for which the baseline manifest subjective refraction exhibits a difference greater than 0.50 D in sphere power, or a difference greater than 0.50 D in cylinder power, or a difference in cylinder axis of more than 15 degrees compared to the baseline cycloplegic subjective refraction. For manifest cylinder of less than 0.50 D, the difference in cylinder axis will not be taken into consideration.

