6.5.6 Analysis of Effectiveness Endpoints

6.5.6.1 Descriptive Statistics and Data Preparation

Statistical programming and analyses will be performed using SAS® Version 9.4 or higher. Output will be provided in rich text format (RTF) for tables and portable document format (PDF) for tables, data listings, and figures using landscape orientation. All study data will be listed by subject, eye, and visit (as applicable) based on all treated subjects unless otherwise specified.

Summaries for continuous and ordinal variables will include the number of observations (n), arithmetic mean, standard deviation (SD), median, minimum, and maximum. Minima

and maxima will be reported with the same precision as the raw values; means and medians will be presented to one additional decimal place than reported in the raw values. Standard deviations will be presented to two additional decimal places than reported in the raw values. Summaries for discrete variables will include counts and percentages. All percentages will be rounded to one decimal place (i.e., XX.X%).

When summarized by visit, nominal visits as indicated on the case report forms will be used. Visit windows will not be considered in the presentation of data by visit.

All statistical tests will be one-sided with a significance level of 0.025 ($\alpha = 0.025$) unless otherwise specified.

Confidence intervals (CIs) around single estimated proportions will be two-sided at 95% confidence.

All p values will be rounded to 4 decimal places; p-values less than 0.0001 will be presented as "<0.0001"; p-values greater than 0.9999 will be presented as ">0.9999."

Unless otherwise specified, summaries will be presented by visit, where appropriate. Data listings will be sorted by subject number, eye, visit/time point, and parameter as applicable.

Baseline is defined as the last measurement prior to LASIK surgery. Change from baseline will be calculated as post-baseline visit minus baseline visit.

Eyes will be treated as independent sampling units ignoring any correlation between the two eyes of each subject, as is customary for LASIK clinical trials.

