6.5.6.3.1 Predictability and Refractive Stability Analyses

The following predictability and refractive stability descriptive summaries will be provided for each visit interval starting with the 1- to 3-month interval and continuing to the 6- to 9month interval for all treated eyes, eyes treated for spherical myopia, and eyes treated for astigmatic myopia unless otherwise specified. Stability analysis will be repeated for Consistent Cohort.

- Eyes that exhibit an absolute change of less than or equal to 0.50 D, 1.00 D, and 2.00 D of MRSE between two refractions performed at 1 month and 3 months, and between subsequent refractions performed at least 3 months apart.
- Mean overall change and change per month (calculated as, Difference in MRSE/ Duration in Months, where month = 30 days) in MRSE between consecutive scheduled visits as determined by a paired analysis, with 95% CIs around the mean rate of change based on t-distribution.
 - The mean rate of change in MRSE is expected to decrease monotonically over time, with a projected asymptote of zero or a rate of change attributable to normal aging.
 - The 95% CI for the mean rate of change in MRSE is expected to include zero or a rate of change attributable to normal aging.
- Mean (\pm SD) MRSE for the preoperative and each postoperative visit
- Proportion of eyes with residual astigmatic error (absolute shift from Preoperative Visit to each postoperative visit in manifest axis versus residual manifest cylinder magnitude calculated as postoperative cylinder value minus targeted cylinder value in categories of ± 0.5 D, ± 1.0 D, ± >1.0 D) will be presented in a table and also stratified by preoperative diopter of cylinder as specified in Table 1 at Month 1, Month 3, Month 6, and Month 9 for eyes treated for astigmatic myopia.
- Assessment of cylinder stability between two refractions performed at 1 month and 3 months, and between subsequent refractions performed at least 3 months apart for correction of spherocylindrical refractive errors, expressed as the proportion of eyes

with an absolute change in cylinder magnitude of 0.00 D, 0.01 D to 0.50 D, 0.51 D to 1.00 D, 1.01 D to 1.50 D, and >1.51 D.

- Vector magnitude correction analysis will be summarized including intended refractive correction (IRC), surgically induced refractive correction (SIRC) and correction ratio (CR) calculated as SIRC/IRC, as defined in the Eydelman M paper

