 [2] and also provided in the appendix. These data by study visit will be presented as continuous summary for all eyes treated for astigmatic myopia.
- Cylinder correction (non-vectorial) stratified by preoperative cylinder as specified in Table 1 for all eyes treated for astigmatic myopia will be summarized on a continuous scale in a table by study visit beginning at Month 1 for percent reduction of absolute IRC.

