6.5.6.5.1 Additional Effectiveness Analyses

The following effectiveness descriptive summaries will be provided at Month 1, Month 3, Month 6, and Month 9. Primary effectiveness endpoint data will be presented using 1.00 D ranges from -1.00 D to -12.00 D (based on Table 1, the maximum MRSE value that is allowed in the study is -11.5 D) and for preoperative MRSE > -7.0 D versus MRSE \leq -7.0 D).

- Percentage of eyes that achieve predictability of MRSE within ± 0.50 D
- Percentage of eyes that achieve predictability of MRSE within \pm 1.00 D

- Percentage of eyes that achieve UCDVA of 20/40 or better
- Percentage of all eyes that achieve predictability (targeted versus achieved) of MRSE within ± 2.00 D
- Percentage of all eyes targeted for emmetropia that achieve UCDVA of 20/12.5 or better, 20/16 or better, 20/20 or better, 20/40 or better
- Percentage of eyes not targeted for emmetropia that achieve UCDVA of 20/20 or better and of 20/40 or better.
- Percentage of eyes that achieve predictability of manifest spherical refraction within $\pm 0.50 \text{ D}, \pm 1.00 \text{ D}$, and $\pm 2.00 \text{ D}$ of intended manifest spherical refraction
- Percentage of eyes with predictability of manifest refraction astigmatism within \pm 0.50 D, \pm 1.00 D, and \pm 2.00 D of intended manifest cylindrical refraction
- Percentage of eyes that achieve an UCDVA equal to or better than preoperative BSCVA, including eyes that achieve an UCDVA equal to or better than 20/40 if the preoperative BSCVA was 20/20 or better
- Change from baseline in BSCVA by study visit
- Change from baseline in UCNVA and UCDVA
- Percentage of eyes that are overcorrected or under corrected by > 1.00 D or > 2.00 D MRSE
- Percentage of eyes that achieve a difference between postoperative and preoperative BSCVA of < -2 lines, -2 lines, -1 line, 0 lines, +1 line, +2 lines, and > +2 lines (line changes will be calculated as integer portion of change from baseline values of Early Treatment Diabetic Retinopathy Study [ETDRS letter] score collected on the CRF divided by 5)
- Percentage of eyes with CR of ≤ 0.5 D and ≤ 1.0 D
- Absolute shift in cylindrical axis from preoperative to postoperative visits of 0, <= 5, 5.1 to 10, 10.1 to 15, 15.1 to 30, and >30 deg.
- Eyes as a function of angle of cylindrical error (based on vector analysis. Refer to Appendix 1 for derivation):
 - Eyes with error of angle \ge -15° and \le +15°
 - Eyes with error of angle greater than $+15^{\circ}$

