7 REFERENCES

1. ANSI Z80.11-2012 (R2017) standard - Laser Systems for Corneal Reshaping

3. LASIK Pre-Operative Questionnaire (PRQ). (2015, June 4). Retrieved from https://www.fda.gov/downloads/MedicalDevices/ProductsandMedicalProcedures/Surgerya ndLifeSupport/LASIK/UCM528837.pdf

4. LASIK Post-Operative Questionnaire (POQ). (2015, June 2). Retrieved from https://www.fda.gov/downloads/MedicalDevices/ProductsandMedicalProcedures/Surgerya ndLifeSupport/LASIK/UCM528841.pdf

6. Engineering Report ER-100022264: Data analysis report of patients with preoperative only spherical myopia or myopic astigmatism, Technolas Document #100022264.

8 APPENDIX 1

Vector analyses

The following pre-analysis transformations will be done:

- 1. Convert manifest refraction to positive cylinder notation.
- 2. Convert all manifest refraction data from the spectacle to the corneal plane (adjusting for vertex distance) using the following formula:

$$MRC = \frac{1000 (Sph + Cyl)}{1000 - 13 (Sph + Cyl)} - \frac{1000 Sph}{1000 - 13 Sph}$$

Where

MRC = Refractive cylinder at the corneal plane Sph = Manifest refractive sphere

- Cyl = Manifest refractive cylinder
- 3. Adjust left eye axis as follows:

Adjusted Axis = $180^{\circ} - Original$ axis

Vector Analysis Variables:

- 1. The intended refractive correction vector (IRC) is defined as the vector difference between the preoperative astigmatic correction vector and the target postoperative cylinder vector (preoperative - target). If the target refractive state is emmetropia, the IRC vector is equal to the preoperative cylinder (i.e., MRC) and angle.
- 2. Surgically induced refractive correction (SIRC) vector is the vector difference between the preoperative and postoperative astigmatic correction vectors (preoperative postoperative).

Methods for calculating the refractive error analysis variables (from here onwards, C = MRC and A for left eye is the adjusted axis):

1. Convert the preoperative astigmatic correction to X and Y vector components:

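### The mean correction ratio over all astigmatic eyes is biased upward by eyes with 0.25-0.50 D of cylinder, and the SAP drops the stratification that would show it

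*SAP*

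**What the plan says.** SAP Section 6.5.6.3.1 defines the ratio in this sentence: "Vector magnitude correction analysis will be summarized including intended refractive correction (IRC), surgically induced refractive correction (SIRC) and correction ratio (CR) calculated as SIRC/IRC". It adds: "These data by study visit will be presented as continuous summary for all eyes treated for astigmatic myopia". Under SAP Section 6.5.6.1 a continuous summary has this content: "Summaries for continuous and ordinal variables will include the number of observations (n), arithmetic mean, standard deviation (SD), median, minimum, and maximum". A median is therefore reported beside the mean.

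SAP Appendix 1 computes SIRC as the length of the difference between the preoperative and postoperative cylinder vectors. For the denominator it says: "If the target refractive state is emmetropia, the IRC vector is equal to the preoperative cylinder (i.e., MRC) and angle". No minimum IRC is set. Table 1 plans at least 30 eyes with 0.25-0.50 D of cylinder and sets no upper limit. Protocol Appendix B, Section 7.0, has refraction done in 0.25 D steps.

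Protocol Section 9.6.3.1 lists the correction ratio among the key effectiveness variables to be stratified by preoperative MRSE and by preoperative cylinder. SAP Section 6.6 withdraws the cylinder stratification. SAP Section 6.5.6.5.1 adds the shares of eyes with a ratio of at most 0.5 and at most 1.0, also without a breakdown by cylinder.

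On the device history, Protocol Section 5.1 says that the "internal cylinder conversion factor for the PROSCAN version 1.27.2 software was increased to compensate for cylindrical under-correction".

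**The concern.** A vector length cannot be negative, so error in any direction lengthens SIRC on average. Dividing by 0.25 or 0.50 D magnifies that excess, and averaging per-eye ratios gives each such eye the same weight as an eye with 3 D.

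Version 1.28 differs from 1.27.2 in its cylinder factor, so readers will look at the cylinder results to see whether the change worked. A mean ratio near 1.0 is naturally read as full correction. If the low-cylinder eyes lift the mean, that reading can be wrong. The table by preoperative cylinder, where the lift would be visible, is the one the SAP removed.

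**Working it through.** **No planned figure to reproduce.** The documents state no expected value, precision or noise level for the correction ratio.

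**Inputs from the documents.** Cylinder bins are those of Table 1, with values in 0.25 D steps. Of at least 300 eyes, at least 30 are sphere-only, which leaves up to 300 - 30 = 270 astigmatic eyes. With at least 30 in each of the four cylinder bins, the low-cylinder bin can hold 30 to 270 - 3 x 30 = 180 eyes.

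**Assumptions.** True correction factor k = 0.90 or 0.85; noise SD s per vector component of SIRC of 0.10-0.25 D, pre- and postoperative error combined; case mixes as labelled.

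**Model.** SIRC = k x IRC along the intended axis, plus bivariate normal noise. The mean length is a Rice mean:

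E|SIRC| = s x sqrt(pi/2) x L(x), with x = (k x IRC)^2 / (2 s^2) and L(x) = exp(-x/2) x [(1 + x) I0(x/2) + x I1(x/2)].

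When IRC is large relative to s, the excess in the ratio is about s^2 / (2 k IRC^2), so it falls with the square of the cylinder.

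**One eye.** Take k = 0.85, s = 0.25 D, IRC = 0.25 D. Then x = 0.2125^2 / 0.125 = 0.361, L = 1.173, E|SIRC| = 0.3133 x 1.173 = 0.3675 D, and the ratio is 0.3675 / 0.25 = 1.47. The same formula gives 1.01 at 0.50 D, 0.89 at 1 D and 0.85 at 3 D.

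**One cohort.** With k = 0.90 and s = 0.20 D, the expected ratios in the four cylinder bins are 1.146, 0.932, 0.909 and 0.903. In a 40/30/20/10% mix the mean is 0.4 x 1.146 + 0.3 x 0.932 + 0.2 x 0.909 + 0.1 x 0.903 = 1.01. Of the excess of 0.110 over 0.90, the lowest bin supplies 0.4 x 0.246 = 0.098, about 89%.

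**Expected mean ratio:**

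| s (D) | k = 0.90, equal bins | k = 0.90, 40/30/20/10% | k = 0.90, 30 of 270 low | k = 0.85, equal bins | k = 0.85, 40/30/20/10% | k = 0.85, 30 of 270 low |
|---|---|---|---|---|---|---|
| 0.10 | 0.92 | 0.93 | 0.91 | 0.87 | 0.88 | 0.86 |
| 0.15 | 0.94 | 0.96 | 0.92 | 0.89 | 0.92 | 0.87 |
| 0.20 | 0.97 | 1.01 | 0.94 | 0.93 | 0.97 | 0.89 |
| 0.25 | 1.01 | 1.07 | 0.96 | 0.97 | 1.03 | 0.92 |

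At s = 0.10 D the mean is at most 0.94 for k = 0.90, even with 180 of 270 eyes low-cylinder.

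Rounding postoperative cylinder to 0.25 D changes these values by about 0.015 or less. The vertex conversion in Appendix 1 raises them somewhat. With 30 of 270 low-cylinder eyes and s = 0.25 D they become 0.98 (k = 0.90) and 0.94 (k = 0.85).

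**Noise at which the mean reads 1.00** (before vertex conversion). With 30 of 270 low-cylinder eyes: 0.32 D for k = 0.90 and 0.39 D for k = 0.85. With equal bins: 0.24 and 0.29 D. With 180 of 270: 0.15 and 0.18 D.

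**Alternatives on the same eyes.** With k = 0.85, s = 0.25 D and 90/90/60/30 eyes per bin, the mean ratio is 1.00. By bin it is 1.24, 0.90, 0.87 and 0.86. Without the lowest bin it is (90 x 0.903 + 60 x 0.865 + 30 x 0.856) / 180 = 0.88. Mean SIRC over mean IRC is 0.91. A slope through the origin of the on-axis SIRC component on IRC returns 0.85.

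**The case against.** The strongest reply is that this is one descriptive row and that neighbouring outputs partly give the bias away. That largely stands. Success rests on the three MRSE and UCDVA endpoints. The median is reported, and mean SIRC over mean IRC can be read from the same table. With 0.25 D rounding, s = 0.15-0.25 D and the first two mixes, the median reads 0.92-1.00 for a true 0.90 and 0.87-0.94 for a true 0.85. The ratio of means reads 0.91-0.965 and 0.865-0.92. But the SAP does not call for that ratio, and the median reaches 1.00 in the most adverse case. The planned percent reduction by cylinder bin is not a substitute, because noise biases it downward: at s = 0.25 D it reads 0.05/0.61/0.76/0.81 for k = 0.85 against 0.06/0.63/0.80/0.88 for a perfect laser.

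A second reply is that the pooled on-axis ratio is not unbiased either. That also stands. The same preoperative refraction enters SIRC and IRC and programs the laser. With the noise split equally between visits, SIRC = k x observed cylinder + preoperative error - postoperative error. The pooled ratio then reads 0.91-0.96 for a true 0.90, while the per-eye mean over all eyes reads 0.95-1.08 (simulated with 0.25 D rounding, s = 0.15-0.25 D, same mixes). The per-eye mean restricted to 0.75 D or more reads 0.92-0.99.

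A reader might also infer that the axis-shift row in SAP Section 6.5.6.5.1 ("Absolute shift in cylindrical axis from preoperative to postoperative visits of 0" and upward) is a separate error, since the axis of a small residual cylinder is nearly random. The documents do not support that. SAP Section 6.5.6.3.1 already tabulates axis shift against residual cylinder. The eligibility rule "For manifest cylinder of less than 0.50 D, the difference in cylinder axis will not be taken into consideration" concerns agreement of preoperative manifest and cycloplegic refractions, not postoperative residuals.

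**Conclusion.** The concern holds as an upward bias in one descriptive summary. Its direction, and its concentration in the 0.25-0.50 D eyes, follow from the SAP's own formulas. Its size rests on an assumed noise SD and case mix, as tabulated above. For 15% under-correction, only one of the six combinations of s = 0.15-0.25 D with the first two mixes reaches 1.0; for 10%, three of six do.

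Three stronger readings go beyond the documents. One is that the mean will read 1.0 and hide under-correction: it can, but not at low noise or, with noise up to 0.25 D, at the planned minimum of low-cylinder eyes. Another is that 10-15% under-correction is expected: Protocol Section 5.1 calls the earlier under-correction slight and gives no figure, so 0.90 and 0.85 are illustrations. The third is that the ratio is the designated test of the cylinder change: no section makes it one or sets a threshold for it. What remains is that a summary bearing on the version 1.28 adjustment is hard to interpret as planned, and the breakdown that would have clarified it was removed.

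**What to change.** 1. Report the correction ratio by the Table 1 preoperative cylinder bins, as Protocol Section 9.6.3.1 planned, and amend SAP Section 6.6 to match.
2. Give the per-eye mean ratio for eyes with preoperative cylinder of 0.75 D or more.
3. Add a pooled cohort ratio: the sum over eyes of (X_SIRC x X_IRC + Y_SIRC x Y_IRC) / |IRC|, divided by the sum of |IRC|. Compute it from the X and Y components, not from the error of angle. Appendix 1 sets that angle to 0 when the axes differ by exactly 90 degrees, which would count an opposite change as fully on-axis.
4. State in a footnote that the pooled ratio is much less biased than the mean of ratios, but still reads slightly high when preoperative refraction error enters both terms.
5. At most, refer the axis-shift row in Section 6.5.6.5.1 to the table of axis shift against residual cylinder in Section 6.5.6.3.1.

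The cost is a few lines of SAP text and code, with no new data and no effect on the primary endpoints.

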6.5.6.4 Secondary Effectiveness Endpoints

There are no secondary effectiveness endpoints.

6.5.6.5 Tertiary/Supportive/Other Effectiveness Assessments

No imputation for missing data methods will be used for the additional effectiveness assessments presented in subsections of this section. All data will be analyzed using available data only.

Effectiveness analyses will be performed for all treated eyes, eyes treated for spherical myopia, and eyes treated for astigmatic myopia, and data listings for measurements of effectiveness will be presented.

6.5.6.5.1 Additional Effectiveness Analyses

The following effectiveness descriptive summaries will be provided at Month 1, Month 3, Month 6, and Month 9. Primary effectiveness endpoint data will be presented using 1.00 D ranges from -1.00 D to -12.00 D (based on Table 1, the maximum MRSE value that is allowed in the study is -11.5 D) and for preoperative MRSE > -7.0 D versus MRSE \leq -7.0 D).

- Percentage of eyes that achieve predictability of MRSE within ± 0.50 D
- Percentage of eyes that achieve predictability of MRSE within \pm 1.00 D

- Percentage of eyes that achieve UCDVA of 20/40 or better
- Percentage of all eyes that achieve predictability (targeted versus achieved) of MRSE within ± 2.00 D
- Percentage of all eyes targeted for emmetropia that achieve UCDVA of 20/12.5 or better, 20/16 or better, 20/20 or better, 20/40 or better
- Percentage of eyes not targeted for emmetropia that achieve UCDVA of 20/20 or better and of 20/40 or better.
- Percentage of eyes that achieve predictability of manifest spherical refraction within $\pm 0.50 \text{ D}, \pm 1.00 \text{ D}$, and $\pm 2.00 \text{ D}$ of intended manifest spherical refraction
- Percentage of eyes with predictability of manifest refraction astigmatism within \pm 0.50 D, \pm 1.00 D, and \pm 2.00 D of intended manifest cylindrical refraction
- Percentage of eyes that achieve an UCDVA equal to or better than preoperative BSCVA, including eyes that achieve an UCDVA equal to or better than 20/40 if the preoperative BSCVA was 20/20 or better
- Change from baseline in BSCVA by study visit
- Change from baseline in UCNVA and UCDVA
- Percentage of eyes that are overcorrected or under corrected by > 1.00 D or > 2.00 D MRSE
- Percentage of eyes that achieve a difference between postoperative and preoperative BSCVA of < -2 lines, -2 lines, -1 line, 0 lines, +1 line, +2 lines, and > +2 lines (line changes will be calculated as integer portion of change from baseline values of Early Treatment Diabetic Retinopathy Study [ETDRS letter] score collected on the CRF divided by 5)
- Percentage of eyes with CR of ≤ 0.5 D and ≤ 1.0 D
- Absolute shift in cylindrical axis from preoperative to postoperative visits of 0, <= 5, 5.1 to 10, 10.1 to 15, 15.1 to 30, and >30 deg.
- Eyes as a function of angle of cylindrical error (based on vector analysis. Refer to Appendix 1 for derivation):
 - Eyes with error of angle \ge -15° and \le +15°
 - Eyes with error of angle greater than $+15^{\circ}$

• Eyes with error of angle less than -15°

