9.6.3 Additional Analyses

9.6.3.1 Additional Effectiveness Analyses

The following effectiveness descriptive summaries will be provided at Month 1, Month 3, Month 6, and Month 9. The summaries will be provided for all eyes, eyes treated for spherical myopia only, and eyes treated for astigmatic myopia. These key effectiveness variables will be presented as listed and also stratified by preoperative MRSE and by preoperative manifest cylinder power:

ΓΕΝΕΟ 317 1.28 US	CONFIDENTIAL

- Percentage of eyes with preoperative myopic MRSE \leq 7.0 D and those > 7.0 D that achieve predictability of MRSE within \pm 0.50 D at the time of refractive stability
- Percentage of eyes with preoperative myopic MRSE \leq 7.0 D and those > 7.0 D that achieve predictability of MRSE within \pm 1.00 D at the time of refractive stability
- Percentage of eyes with preoperative myopic MRSE \leq 7.0 D and those > 7.0 D that achieve UDVA of 20/40 or better at the time of refractive stability
- Percentage of all eyes that achieve predictability (attempted versus achieved) of MRSE within ± 2.00 D
- Percentage of all eyes targeted for emmetropia that achieve UDVA of 20/12.5 or better, 20/16 or better, 20/20 or better, 20/40 or better
- Percentage of eyes not targeted for emmetropia that achieve UDVA of 20/20 or better and of 20/40 or better.
- Percentage of eyes that achieve accuracy of manifest spherical refraction within \pm 0.50 D, \pm 1.00 D, and \pm 2.00 D of intended manifest spherical refraction
- Percentage of eyes with accuracy of manifest refraction astigmatism within ± 0.50 D, ± 1.00 D, and ± 2.00 D of intended residual cylinder power
- Percentage of eyes that achieve an UDVA equal to or better than preoperative BSCVA, including eyes that achieve an UDVA equal to or better than 20/40 if the preoperative BSCVA was 20/20 or better
- Change from baseline in BSCVA by study visit
- Change from baseline in UCNVA and UDVA
- Percentage of eyes that are overcorrected or under corrected by > 1.00 D or > 2.00 D
- Percentage of eyes that achieve a difference between postoperative and preoperative BSCVA of < -2 lines, -2 lines, -1 line, 0 lines, +1 line, +2 lines, and >+2 lines
- Change in subjective Patient Reported Outcome questionnaire scores (see Section 9.6.3.3.1)
- Correction ratio (CR) = surgically induced refractive correction (SIRC)/intended refraction correction (IRC)
- Absolute shift in cylindrical axis at stability time point

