6.5.4.2 Baseline Refractive Parameters

The preoperative bin distribution of enrolled eyes by sphere and cylinder is based on the preoperative manifest refraction, specifically sphere and cylinder. All eyes will be treated for myopia with a target refraction of emmetropia. All eyes enrolled and treated will have at least -1.0 D of spherical myopia or more and at least 0.0 D or more of cylinder in the study. Table 1, above, provides the expected bin distribution stratified by preoperative sphere and cylinder. Tables will be provided of preoperative bin distributions for all treated eyes, eyes treated for spherical myopia, and eyes treated for astigmatic myopia. A data listing of preoperative sphere and cylinder by subject also will be provided. Sphere and cylinder values will be converted to minus notation for presentation and subsequent analysis in the efficacy section as follows:

If the Original Cylinder <= 0, then no conversion is necessary.

If the Original Cylinder > 0 then

New Sphere = Original Sphere + Original Cylinder

New Cylinder = - Original Cylinder

New Axis = Original Axis - 90, if Original Axis > 90

Original Axis + 90, if Original Axis \leq 90

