 $X_{preop} = C_{preop} * \cos(2*A_{preop})$ $Y_{preop} = C_{preop} * \sin(2*A_{preop})$

2. Convert the postoperative astigmatic correction to X and Y vector components:

 $X_{postop} = C_{postop} * \cos(2*A_{postop})$ $V_{postop} = C_{postop} * \sin(2*A_{postop})$

$$Y_{postop} = C_{postop} * \sin(2*A_{postop})$$

3. Find the magnitude of the SIRC

 $|SIRC| = \sqrt{[Xpreop - Xpostop]^2 + [Ypreop - Ypostop]^2}$

4. Find the axis of the SIRC, A_{SIRC} , using the preoperative and postoperative X and Y comments (where $X_{SIRC} = X_{preop} - X_{postop}$ and $Y_{SIRC} = Y_{preop} - Y_{postop}$).

$$\theta = 0.5 * \arctan\left[\frac{\text{YSIRC}}{\text{XSIRC}}\right]$$

- Then, find A_{SIRC} using the X and Y components of SIRC:
 - If $Y_{SIRC} \ge 0$ and $X_{SIRC} > 0$ then $A_{SIRC} = \theta$

If $Y_{SIRC} < 0$ and $X_{SIRC} > 0$ then $A_{SIRC} = \theta + 180^{\circ}$

If $X_{SIRC} < 0$ then $A_{SIRC} = \theta + 90^{\circ}$

```
If X_{SIRC}=0 and Y_{SIRC}>0 then A_{SIRC}=45^{\circ}
```

If
$$X_{SIRC}=0$$
 and $Y_{SIRC}<0$ then $A_{SIRC}=135^{\circ}$

5. Find error of angle (EA) by subtracting A_{IRC} from A_{SIRC} .

 $EA = A_{SIRC} - A_{IRC}$, if $|A_{SIRC} - A_{IRC}| < 90^{\circ}$

- $EA = A_{SIRC} A_{IRC} 180^\circ$, if $A_{SIRC} A_{IRC} > 90^\circ$
- $EA = A_{SIRC} A_{IRC} + 180^\circ$, if $A_{SIRC} A_{IRC} < -90^\circ$
- $EA = 0^\circ$, if $A_{SIRC} A_{IRC} = \pm 90^\circ$.

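### Two rules behind the SAP's descriptive astigmatism tables need correcting: an axis error of exactly 90° is scored as 0°, and the unitless correction ratio is tabulated in diopters for an unstated population

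*SAP*

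**What the plan says.** **Error of angle.** SAP Appendix 1 converts refractions to plus cylinder and moves them to the corneal plane: "Convert all manifest refraction data from the spectacle to the corneal plane (adjusting for vertex distance"). It forms the intended (IRC) and surgically induced (SIRC) correction vectors. Step 5 begins "Find error of angle (EA) by subtracting" the IRC axis from the SIRC axis. Differences below 90° in size are kept, and those beyond +90° or -90° are shifted by 180°. The last branch reads, in the machine-read text, "EA = 0^\circ$, if $A_{SIRC} A_{IRC} = \pm 90" (degrees). The minus sign between the two axes was lost in reading, but the assignment of 0° is explicit.

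SAP 6.5.6.5.1 uses the result: "Eyes as a function of angle of cylindrical error (based on vector analysis. Refer to Appendix 1 for derivation"). Its rows are -15° to +15°, above +15° and below -15°.

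**Target.** SAP 6.5.4.2 states "All eyes will be treated for myopia with a target refraction of emmetropia". Appendix 1 adds "If the target refractive state is emmetropia, the IRC vector is equal to the preoperative cylinder" and its angle.

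**Correction ratio.** Protocol 9.6.3.1 gives "Correction ratio (CR) = surgically induced refractive correction (SIRC)/intended refraction correction (IRC"), and SAP 6.5.6.3.1 defines CR the same way. SAP 6.5.6.5.1 nevertheless asks for "Percentage of eyes with CR of ≤ 0.5 D and ≤ 1.0 D".

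**Population.** SAP 6.5.6.5 runs its effectiveness analyses for all treated eyes, spherical-myopia eyes and astigmatic-myopia eyes. SAP 6.5.6.3.1 limits the continuous vector summary (IRC, SIRC, CR) to astigmatic eyes; the CR and EA rows in 6.5.6.5.1 carry no such limit. SAP 6.6 comments on none of this.

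**The concern.** EA tells the reader whether the correction was applied along the intended axis. Axes repeat every 180°, so 90° is the worst possible value. Giving it the score for perfect alignment makes EA jump: a difference of 89.9° stays 89.9°, 90° becomes 0°, and 90.1° becomes -89.9°. Same-axis cylinder growth produces exactly this case, so such eyes would be reported with the well-aligned ones, an error in the favourable direction.

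Protocol 5.1 says the cylinder conversion factor was raised for this software version, so these tables bear on what changed.

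The CR row gives diopters to a ratio and is nominally produced for eyes in which the ratio does not exist. A programmer has to settle both points without help from the text.

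**Working it through.** No figure in the plan corresponds to this check, so I coded Appendix 1 as written and ran example eyes through it.

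**Inputs.** Emmetropic target (SAP 6.5.4.2). Corneal-plane cylinder MRC = 1000(S+C)/(1000-13(S+C)) - 1000S/(1000-13S), in plus-cylinder form (Appendix 1). X = MRC·cos 2A and Y = MRC·sin 2A. IRC = preoperative vector; SIRC = preoperative minus postoperative vector.

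**Same-axis growth by algebra.** With the axis unchanged, SIRC lies along the preoperative direction with signed size (preoperative MRC - postoperative MRC). If the cylinder grew, this is negative. SIRC then points opposite to IRC in double-angle space, which is an axis difference of 90°.

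**Worked eye, -3.00 -0.50 x 90 to plano -1.00 x 90.**
- Preoperative plus form -3.50 +0.50 x 180: MRC = -3000/1039 + 3500/1045.5 = -2.8874 + 3.3477 = 0.460 D.
- Postoperative plus form -1.00 +1.00 x 180: MRC = 0 + 1000/1013 = 0.987 D.
- X_SIRC = 0.460 - 0.987 = -0.527 and Y_SIRC = 0, so |SIRC| = 0.527 D.
- X_SIRC is negative, so A_SIRC = 0 + 90 = 90°. A_IRC = 180°. The difference is -90°, so **EA = 0°**.
- CR = 0.527/0.460 = 1.145.

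Read together, CR 1.145 and EA 0° suggest slight overcorrection on the right axis, yet the corneal-plane cylinder more than doubled.

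**Same eye, postoperative axis 91.** X_SIRC = 0.4603 - 0.9872·cos 2° = -0.5263 and Y_SIRC = -0.9872·sin 2° = -0.0345. A_SIRC = 0.5·arctan(0.0655) + 90 = 91.87°, the difference is -88.13°, and EA = -88.1°. With axis 95, EA = -80.7°.

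**Second eye, -3.00 -1.00 x 90 to plano -1.50 x 90.** Cylinder 0.915 to 1.471 D, SIRC 0.556 D, CR 0.608, EA 0°. With axis 91, EA = -87.4°.

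**Rounding.** The rule tests exact equality on an arctangent result. For -3.00 -0.50 to plano -0.75 on the same axis, it returned 0° at 162 of 180 whole-degree axes in unrounded floating point, and at all 180 after rounding the difference to 6 decimals. The arithmetic implementation alone can therefore move an eye between rows.

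**Could a SIRC threshold of one 0.25 D refraction step identify eyes with negligible induced correction?** Not reliably:
- Grown by one step: -1.00 -0.25 to -0.50 -0.50, same axis. MRC 0.2428 to 0.4904, SIRC 0.248 D.
- Grown by one step: -1.00 -1.00 to -1.00 -1.25, same axis. MRC 0.9622 to 1.1989, SIRC 0.237 D.
- Manifest cylinder unchanged: -3.00 -0.50 to plano -0.50. SIRC 0.036 D, from the vertex conversion alone.
- Manifest cylinder unchanged: -10.00 -3.00 to plano -3.00. MRC 2.271 to 2.887, SIRC 0.616 D.

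Grown eyes can fall below 0.25 D, and unchanged eyes can lie above it.

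**CR unit.** Diopters cancel in SIRC/IRC. The reading matters: IRC 2.0 D with SIRC 1.0 D gives CR 0.50, which meets ≤ 0.5, but |IRC - SIRC| = 1.0 D, which fails ≤ 0.5 D. IRC 2.5 D with SIRC 2.4 D gives CR 0.96 (fails) but |IRC - SIRC| = 0.1 D (meets).

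**CR population.** A -3.00 D eye with zero cylinder and an emmetropic target has IRC = 0. CR divides by zero and A_IRC does not exist. SAP Table 1 plans at least 30 such zero-cylinder eyes among at least 300.

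**The case against.** A reader might infer that the CR rows cannot be programmed as written. The documents do not support that. Both define CR as a ratio and neither defines a diopter version. SAP 6.5.6.5.1 already has separate diopter rows for cylinder predictability. SAP 6.5.6.3.1 gives the astigmatic population for the same vector quantities, and SAP 6.5.6.5 uses available data only, so an undefined CR could simply drop out. This half of the point is a clarification.

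A reader might also infer that alignment will be materially overstated. The documents give no basis for a count. The trigger needs corneal-plane cylinder not merely to grow but to do so on exactly the same recorded axis; one degree of change avoids it. Other planned outputs still show the growth: residual cylinder, cylinder predictability and percent cylinder reduction.

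The EA part rests on one machine-read line, and the surrounding formulas show reading damage. The other three branches leave exactly ±90° uncovered, which fits a deliberate separate rule. If it is deliberate, it may be a convention taken from the paper that SAP 6.5.6.3.1 cites for its vector definitions; that cannot be checked here. This lowers confidence without removing the point: a convention that scores the worst alignment as the best still misplaces these eyes, and the SAP gives no reason for it.

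**Conclusion.** The point holds as a low-severity correction, one the sponsor could make. Confidence is moderate for the EA rule, subject to checking the line in the PDF, and high for the CR unit.

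As written, step 5 places eyes with same-axis cylinder growth in the ±15° row when a one-degree axis change would put the worked eyes beyond 87°. This assumes an emmetropic target and the Appendix 1 vertex conversion. The CR row carries a unit the quantity does not have, and the CR and EA rows lack a population statement that excludes eyes with IRC = 0.

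The effect stops at descriptive astigmatism tables. The three primary endpoints use MRSE and uncorrected distance acuity, so their tests and the success rule are untouched.

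**What to change.** 1. **Step 5.** Check the line against the PDF. If it reads as above, replace it: when the axis difference is 90° within a small stated tolerance (0.01° would do), set |EA| = 90° and count the eye outside the ±15° row. The sign at 90° is arbitrary, so state where such eyes are shown, for instance in a row of their own.
2. **If 0° was meant for eyes with negligible induced correction,** say so and use an explicit SIRC threshold, justified and fixed before database lock. One 0.25 D step is not a safe default, as shown above.
3. **CR row.** Delete the D. If a diopter quantity was meant, name it and tabulate that instead.
4. **Population.** State that the CR and EA rows cover only eyes treated for astigmatic myopia, with IRC above 0.

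The cost is a few lines of SAP text and reprogramming of two outputs, with no new data. The downside is that a few eyes may leave the within-15° row.
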